Patients are advised to take their time reading the consent forms; they may leave and return to them and reread sections if they'd like to. To mitigate any potential difficulties related to readability (i.e. length of the document, screen size, small text) and to ensure participants understand the most critical aspects of their participation in the study, we will preface the full text of the consent form with a bulleted list, highlighting in plain language the following sections: what the study is about, how we will protect their confidentiality, benefits and risks involved, remuneration, voluntary nature of participation, their participation and their healthcare, and contact information for questions. Subjects will also be able to listen to a verbatim recording of each consent form using a screen reader. If the subject has not agreed to the informed consent after two weeks, he or she will no longer be able to join the study and all data collected during the screening process will be destroyed (except age, biological sex, and reason for exclusion, per CONSORT standards). A copy of the consent form will be accessible to the study coordinator via the Tula server. Subjects can refer to the consent forms electronically by navigating to the Study Information sections of Tula. They will also be able to email the consent form to themselves. If a subject declines to participate at any time during the consent process, he or she may select a "I choose to not participate" button that will ask them why and return them to the launch screen. Reasons for refusal will be noted, in line with CONSORT standards.⁵⁷ Subjects who choose not to disclose why they are ending their participation in the study will also be able to say "I choose not to respond" or "none." All subjects will be reminded that they are under no obligation to participate in this study and can withdraw from the study at any time. They are also told that their health care will not be affected by their participation in this study. Once subjects opt out of the study, they will no longer have access to Tula.

Randomization. Randomization will be done by the study coordinator using the urn randomization program and happen prior to informed consent #2. Study staff will access the admin tool within Tula to assign patients to the self-monitoring, peer-supported, or clinically integrated groups. Randomization will be done in block randomization by clinic, sex, and severity of alcohol use.

Protocol

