Patient and clinician decision making	Value and decision framing survey	Patient/ clinician survey	9	Patient: Pretest, 12 months Clinician: during interview at month 36
Mediators				
Relatedness	CHESS Bonding Scale ^{48,65}	Patient survey	5	
Competence	Perceived Competence Scale	Patient survey	4	0, 3, 6, 9, 12 mo.
Autonomous motivation	TSRQ ⁶⁶	Patient survey	6	
Tula use (patients)	Number of days used, number of pages viewed	Server log files	NA	Continuous
Moderators				
Patient characteristics	Race, ethnicity, gender, age	Patient survey	NA	Pretest

Protocol

HS IRB #2019-0337
Version 5. 10/17/19
Version 6. 04/07/20
Version 7. 10/09/20
Version 8. 01/26/21
Version 9. 08/18/21
Version 10. 07/13/23

All survey data collected through Tula is housed on CHESS servers then exported to the UW sponsored Google Drive folder for statistical analyses.

Screening survey: People interested in participating in the study will be directed to take a Qualtrics screening survey hosted on the Web to determine if they are eligible to participate in the study.

Baseline survey. After patient subjects are enrolled in the study, they will be asked to take a baseline survey consisting of demographic questions, medical service utilization, quality of life, a modified version of the Brief Alcohol Monitor, the CHESS bonding scale, the alcohol competence scale, the TSRQ, and the value of Tula. Data from the screening survey will be used as baseline data for the AUDIT, AUD DSM-5, and timeline follow-back. Two additional questions related to the impact of COVID-19 on participants' physical and mental health will be added to the quality of life measures. These questions will operate on a 5-point Likert scale and will be included across all CHESS studies. (See supporting document "4.6.20 Global Health Scale v1.3_COVID.docx").

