7.0 STUDY PARAMETERS

Patients will be block randomized by clinic, sex, and alcohol use severity to control for demographics at a 1:1:1 ratio to be in the self-monitoring, peer-supported Tula, or clinically integrated Tula groups. It's anticipated that 3-7 clinics (defined as having at least 10 patients in the study) with 3-7 clinicians each and 546 patient subjects will be recruited from the participating UW Health clinics. Patients will have access to Tula for up to 48 months, depending on time of enrollment, although the active period of participation is defined as 3 months with follow up through 12 months post enrollment (9 month follow-up). Health coaches will have access to patient-shared Tula data from patients of the clinically integrated Tula group for the duration of the study. The peer mentor will have access to discussion boards and private messages on Tula for the duration of the study for patients in the peer-supported

Protocol
HS IRB #2019-0337
Version 5. 10/17/19
Version 6. 04/07/20
Version 7. 10/09/20
Version 8. 01/26/21
Version 9. 08/18/21
Version 10. 07/13/23

group. The research team will have access to all Tula data for all subjects in all groups for the duration of the study.

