8.0 STATISTICAL CONSIDERATIONS

Analyses will assess the effectiveness between the three groups longitudinally on the primary and secondary outcomes.

Descriptive analyses. The research team will use descriptive statistics for all demographic and clinical variables across all three arms. To assess the impact of chance baseline imbalances between arms on intervention effect estimates, variables with noticeable differences will be included as covariates in a sensitivity analysis.

Intervention analyses. The analysis assesses direct treatment effects on patient outcomes over time over the 12-month study period. The research team will construct a longitudinal model of our outcome measures at 0, 1, 2, 3, 4, 5, 6, 7, 8, 9, 10, 11, and 12 months after randomization. The stratification variables will be by clinic, biological sex, and alcohol severity. They will be included as factors in the model and the baseline values of patient outcomes will be included as covariates, with a separate model for each primary outcome (risky drinking patterns, quality of life, and cost). This longitudinal analysis is complicated by the dependence among successive observations made on the same individual. Since complete control of measurement is not possible, there may be incomplete data from individual subjects. Therefore we will conduct a mixed-model analysis of repeated measures based on the general linear model with assessment of various covariance structures (compound symmetric, autoregressive order one, and unstructured). Covariance structure selection will be based on Akaike's information criterion and Schwarz's Bayesian criterion.^{46, 47} Pairwise comparisons between treatment groups and specific treatment time contrasts in the mixed model will be conducted to respond to between-group effects and time-based effects. To address issues of incomplete data we plan to estimate treatment effects according to 4 approaches: intention-to-treat, as-treated, per-protocol, and complier-average causal effect. Missing data patterns will be established from the longitudinal data and will be used to adjust the longitudinal intervention analysis according to pattern-mixture modeling.⁶⁹

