Mediation analysis. To augment the intervention analysis, we will estimate the effects that mediating variables have on the outcomes. Services in Tula were developed to meet three psychological needs (competence, relatedness, and autonomous motivation) and accordingly the research team will use a mediational model in which patients in the clinically integrated Tula group will improve these psychological needs, relative to the peer-supported Tula group and the self-monitoring group. In turn, the research team will analyze whether improvements in the psychological needs correlates to improved patient outcomes. Analyses will control for baseline scores on outcome variables and the design variables that are used to stratify our sample during randomization (site). The research team will use structural equation models to assess both direct and indirect influences of our intervention on patient outcomes.⁷⁰ To test the mediation effects via the 3 psychological needs, a mediation model

Protocol

HS IRB #2019-0337
Version 5. 10/17/19
Version 6. 04/07/20
Version 7. 10/09/20
Version 8. 01/26/21
Version 9. 08/18/21
Version 10. 07/13/23

will be constructed to test the mediation effects between randomization variable and 12-month patient outcomes.

Operational cost analysis. Costs will be calculated based on tenets of engineering economics. This study will use incremental cost effectiveness ratios (ICERs) to quantify the tradeoff between the additional effectiveness achieved through clinical integration of the clinically integrated group compared to the peer-supported group. The main ICER will be the incremental cost per reduced drinking days over the 12-month period. We will train the health coach in the clinically integrated group to simulate use of CMS billing codes for mHealth to estimate potential reimbursement potential of the system that may be used to offset the costs of implementation.

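### The mediation analysis names one of three stratification factors, leaves out baseline mediator scores and gives no mediator visit, so its indirect effects may be biased

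*Combined protocol and SAP*

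**What the plan says.** The mediation paragraph of Section 8.0 gives this covariate rule: "Analyses will control for baseline scores on outcome variables and the design variables" used for stratification. The parenthesis that explains those variables contains the single word site: "the design variables that are used to stratify our sample during randomization (site").

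The stratification is described in three other places, each time with three factors:
- Section 4.0, Randomization: "Randomization will be done in block randomization by clinic, sex, and severity of alcohol use".
- Section 7.0: "Patients will be block randomized by clinic, sex, and alcohol use severity to control for demographics at a 1:1:1 ratio".
- Section 8.0, Intervention analyses: "The stratification variables will be by clinic, biological sex, and alcohol severity". Here all three enter the main model as factors.

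On the mediators, Section 8.0 will examine "whether improvements in the psychological needs correlates to improved patient outcomes". A model "will be constructed to test the mediation effects between randomization variable and 12-month patient outcomes". No visit is named for the mediator, and improvement is not defined as a change score, a baseline-adjusted level or anything else.

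The data exist. The baseline survey in Section 5.0 includes "the CHESS bonding scale, the alcohol competence scale, the TSRQ". The quarterly surveys from month 3 repeat all three scales, and Table 1 shows months 0, 3, 6, 9 and 12 (printed on the competence row, apparently for all three mediators).

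**The concern.** A mediation analysis has two links. Random allocation protects the first, from arm to mediator. It does not protect the second, from mediator to outcome, because patients are not randomised to their level of competence, relatedness or motivation. That link depends on the covariates chosen and on the mediator being measured before the outcome. A covariate left out here can cause confounding as well as lost precision.

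Severity and the baseline mediator are the obvious candidates. A patient with milder drinking who starts out more motivated may score higher on motivation later and also drink less at month 12, whatever the app does. Mediation by the three needs is a named secondary aim in Section 2.0, and Section 1.0 relies on it to explain how the intervention works. As the text stands, two analysts could fit different covariate sets and different mediator visits, and both could claim to follow the plan.

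**Working it through.** **Step 1: the text, side by side.**

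| Item | Elsewhere in the protocol | Mediation paragraph |
|---|---|---|
| Stratification factors | Clinic, sex, severity (4.0, 7.0, 8.0) | Site only, in the parenthesis |
| Baseline outcome | Covariate in the main model | Covariate |
| Baseline mediators | Collected (5.0) | Not mentioned |
| Mediator visit | Months 0, 3, 6, 9, 12 available (Table 1) | Not stated |
| Outcome visit | – | Month 12 |

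**Step 2: could the gap matter numerically?** The plan has no effect size or sample size for mediation, so there is no figure to reproduce. The large-sample simulation (1,000,000 records per scenario) rests on assumed paths that are not in the documents. T is arm (0/1), sex is coded ±0.5, severity S is standard normal, M0 and M3 are the mediator at baseline and month 3, Y0 and Y12 are the outcome, and each e is a standard normal error. Clinic was not simulated.

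- M0 = s·sex − 0.3·S (the S term only where v > 0) + e
- Y0 = 0.5·S − m·M0 + s·sex + e
- M3 = 0.3·T + 0.5·M0 + s·sex − v·S + 0.8·e
- Y12 = −0.2·M3 − 0.1·T + 0.4·Y0 − m·M0 + s·sex + v·S + e

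Here m, s and v are the assumed paths for baseline mediator, sex and severity. The true indirect effect is 0.3 × (−0.2) = −0.06. Bias is estimate / (−0.06) − 1; for example −0.0829 / −0.06 = 1.38, or +38%.

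| Paths (m, s, v) | Y0 only | + sex, severity | + baseline mediator |
|---|---|---|---|
| 0, 0, 0 | −0.0603 (+1%) | −0.0603 (+1%) | −0.0602 (0%) |
| 0.1, 0, 0 | −0.0769 (+28%) | −0.0769 (+28%) | −0.0602 (0%) |
| 0.2, 0, 0 | −0.0935 (+56%) | −0.0933 (+56%) | −0.0607 (+1%) |
| 0, 0.1, 0 | −0.0594 (−1%) | −0.0606 (+1%) | −0.0601 (0%) |
| 0, 0.2, 0 | −0.0546 (−9%) | −0.0595 (−1%) | −0.0592 (−1%) |
| 0, 0, 0.1 | −0.0663 (+11%) | −0.0599 (0%) | −0.0600 (0%) |
| 0, 0, 0.2 | −0.0766 (+28%) | −0.0598 (0%) | −0.0599 (0%) |
| 0.1, 0.1, 0.1 | −0.0829 (+38%) | −0.0775 (+29%) | −0.0606 (+1%) |
| 0.2, 0.2, 0.2 | −0.1023 (+71%) | −0.0927 (+55%) | −0.0600 (0%) |

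The first row is the null case, and its 1% is simulation error. Severity and the baseline mediator carry the bias. Sex alone does little, and its sign follows from the direction assumed.

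**Step 3: if improvement means a change score.** Suppose Y depends on the later mediator level with coefficient b, the mediator has variance σ² at both visits and correlation ρ between them, and other covariates are ignored. Then cov(Y, change) = bσ²(1 − ρ) and var(change) = 2σ²(1 − ρ), so regressing on change alone returns b/2. A change score without its baseline is therefore not a substitute for adjustment. With M0 in the model the choice no longer matters, because b·M3 + c·M0 = b·(M3 − M0) + (b + c)·M0.

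**Step 4: if the mediator were taken at month 12.** Assume no true mediation, a total effect of 0.23 SD, and an outcome that drives the mediator with paths 0.1, 0.2 and 0.3. The apparent indirect effects are −0.0024, −0.0096 and −0.0184, or about 1%, 4% and 8% of the total effect.

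**The case against.** The plan is better than a quick reading suggests, and several stronger conclusions do not follow from it.

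- A reader might infer that the model controls for site alone. It does not: the same sentence adjusts for baseline outcome scores. In a drinking model these carry part of the severity information. They carry less in the quality-of-life model, and Section 8.0 fits a separate model for each primary outcome.
- A reader might infer that sex and severity were dropped on purpose. The sentence commits to the variables used for stratification, which elsewhere include both, so the parenthesis may simply be incomplete or outdated. The documents prove an inconsistency, not a decision.
- A reader might infer a month-12 mediator, measured alongside its outcome. No section says so; the visit is unspecified. Step 4 also suggests that reverse causation would be modest under those assumptions.
- A reader might infer that the indirect effects are certain to be biased, or about doubled. Bias needs omitted variables that affect both mediator and outcome, or reverse causation. Doubling needs particular paths. Take a severity association with the baseline mediator of −0.3, severity to outcome 0.25, baseline mediator to later mediator 0.6, and a true mediator effect of −0.10. Adjusting for baseline outcome alone then gives about −0.11 to −0.14, and adding severity restores −0.10. Reaching −0.21 (−0.16 after severity, −0.10 after the baseline mediator) takes a further assumed direct path of about −0.10 from baseline mediator to outcome.

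These points limit the claim but do not remove it. On any reading the parenthesis conflicts with three other passages, the baseline mediators are absent from the covariate rule, and the order of mediator and outcome is left open.

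**Conclusion.** The point holds as an inconsistency and a gap in a secondary analysis. The covariate rule does not match the stated stratification, it leaves out baseline mediator scores that are collected, and it does not require the mediator to precede the 12-month outcome. The indirect effects may be biased as a result.

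The size cannot be taken from the documents. Under the assumed paths it runs from about −9% to +71% with baseline-outcome adjustment only. It is nil when the omitted variables have no direct path to the outcome and the mediator is analysed as a level. Where such paths were assumed, the fuller covariate set removed the bias to within simulation error. Confidence is high on the text mismatch and moderate on its practical effect. The mediator visit is mainly a matter of specification. The primary treatment comparison and the sample size are not affected.

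**What to change.** In the mediation paragraph of Section 8.0:

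1. Replace the word site in the parenthesis with clinic, biological sex and alcohol severity, matching Sections 4.0 and 7.0 and the intervention model.
2. Add the baseline score of each mediator (competence, relatedness, autonomous motivation) as a covariate. This also settles whether improvement means a level or a change.
3. Name a mediator visit before month 12. Month 3, the end of the active period, is one reasonable choice, with months 6 and 9 as sensitivity analyses.
4. Preferably, state the assumption of no unmeasured mediator–outcome confounding and add a sensitivity analysis for it, since measured covariates cannot guarantee it.

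The cost is a few lines of text and, for item 4, a little extra analysis. Every variable is already scheduled for collection. The change should be dated before any mediation results are seen.

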Secondarily, we want to detect differences between groups in health system use, whether patients’ sex (male/female) moderates outcomes, whether effects are mediated by measures of competence, relatedness, and autonomous motivation, and whether levels of use of Tula correlate to changes observed in health outcomes (i.e., dose/response relationship). The study is designed to isolate and examine the role of the clinician in delivering an mHealth system. The cost-effectiveness of each approach will be assessed. This research examines a unique and promising mHealth system with potential clinical, economic, and societal importance and aims to determine the most cost-effective strategy for implementing mHealth into primary healthcare systems.

Protocol
HS IRB #2019-0337
Version 5. 10/17/19
Version 6. 04/07/20
Version 7. 10/09/20
Version 8. 01/26/21
Version 9. 08/18/21
Version 10. 07/13/23

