2.0 STUDY OBJECTIVES

This project proposes a hybrid type II effectiveness/implementation trial that will test the effect on risky drinking patterns and quality of life associated with patient use of an mHealth system under a variety of implementation

Primary Aim:

Detect the effectiveness of interventions by assessing the difference in self-reported risky drinking patterns and quality of life between subjects in the three study groups (self-monitoring, peer-supported, and clinically integrated groups).

Secondary Aims:

Because the study is designed to investigate both the effectiveness of Tula in primary care and the comparative effectiveness of different implementation strategies, the following secondary goals complement study's primary aims:

- Understand the significance clinician monitoring has on alcohol use interventions and patient outcomes.
- Calculate the costs of health system use for each group.
- Develop an mHealth reimbursement strategy prototype using CMS billing codes in the clinically integrated group.
- Understand the degree to which sex moderates the intervention outcomes among Tula users.
- Understand the degree to which patient competence, relatedness, and autonomous motivation (three tenets of self-determination theory) mediate the intervention effect in the Tula groups.
- Assess the dose/response relationship between Tula use and degrees of outcomes
- Understand the impact clinician monitoring has on AUD treatment.
- Qualitatively assesses clinician engagement and clinic needs to further refine Tula and its associated integration for future implementation and dissemination.

Sub-aim:

- Understand the relationship between pain and alcohol consumption after the 3-month active intervention.

Study Coordination

The Implementation Science and Engineering Lab is the coordinating site for this study. The UW study coordinator will oversee all activities at participating UW Health recruitment sites. Activities include:

- developing site-specific recruitment and data collection processes that meet study objectives;
- training the health coaches on protocol procedures prior to the start of recruitment and continuous monitoring to assure compliance with the protocol and human subjects regulation;
- communicating with site staff via regular conference calls to monitor progress, inform of protocol

Protocol

HS IRB #2019-0337
Version 5. 10/17/19
Version 6. 04/07/20
Version 7. 10/09/20
Version 8. 01/26/21
Version 9. 08/18/21

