5.0 INTERVENTION PLAN

All patients enrolled in the study will participate in a 3-month intervention period followed by a 9-month follow-up period, for a total of 12 months. Patients are allowed to continue using Tula after the 12-month period, but will not be asked survey questions after 12 months. Please note that Tula is not a treatment—it is a resource used to help patients reduce their drinking.

All patient subjects will undergo a 72-hour run-in period when they will have access to the basic version of Tula. During this period, potential subjects will be asked to complete the Quick Start checklist items within the 72 hours. The checklist tasks are completing the baseline survey; setting goals for the 90-day active intervention period related to drinking and, optionally, to other aspects of health (e.g., sleep, exercise); completing the first weekly survey; and completing a survey called What Matters to Me, which helps patients think about their current health status and what they would like to change. After 72 hours, patient subjects who complete these tasks will be randomized to one of three groups and receive the appropriate access to Tula features.

Patients in all three groups—regardless of randomization group—will have access to the same static content on Tula, which is described in Section 1, Background and Significance. In addition, patients in all three groups will be asked to complete (1) a weekly survey during the active intervention period and, optionally, to revise the goals they set during the run-in period and (2) quarterly surveys at month 3, 6, 9, and 12. Subjects are free not to answer any survey questions.

Self-monitoring (control) group. Patients of this group will continue receiving regular care from their physician with no interference from the two experimental groups. No data will be shared with other participants. Only the research team will have access to subject data for evaluation purposes.

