6.0 MEASUREMENT OF EFFECT

All scales have good psychometric properties with similar populations. Listed below are the factors to be measured and measurement instruments.

Intake only. Study staff will confirm patient eligibility via patients' UW Qualtrics screening surveys . Patients report demographics (biological sex, race, ethnicity, age, education).

Protocol
HS IRB #2019-0337
Version 5. 10/17/19
Version 6. 04/07/20
Version 7. 10/09/20
Version 8. 01/26/21
Version 9. 08/18/21
Version 10. 07/13/23

Drinking and quality of life. Patients will be asked to take surveys administered via the Tula app (see Table 1 for frequencies). Patients will be asked to report on their drinking using the 7-day timeline follow-back^{58,59} survey. Patients will also take the PROMIS Global Health⁶⁰ survey (10 items) to assess patient self-reported quality of life and a modified version of the Brief Alcohol Monitor⁶³ survey (10 items) to assess their risk and protection factors for problematic alcohol use. Alcohol use disorder severity (AUD scale,⁶⁴ 11 items; AUDIT, 10 items; 7-day timeline followback, 5 items) will be assessed at baseline and once every 3 months.

Mediators. Self-determination theory constructs will be assessed (see Table 1 for frequencies) via the Tula app as follows:

- Competence – Perceived Competence Scale (4 items)
- Relatedness – CHESS Bonding Scale^{65,66} (5 items)
- Autonomous motivation – revised Treatment Self Regulations Questionnaire⁶⁷ (6 items)

Tula use. Tula use is collected in time-stamped log files and includes when a patient accessed Tula, the services used, duration of service use, pages viewed, messages posted and received, and content of messages. Tula use will be used to measure dose of intervention received for dose/response analyses. Patients will be asked to take a survey about their value of Tula at baseline and 12 months.

Healthcare utilization. Healthcare utilization will be collected from the self-reported medical services utilization form⁶¹ (6 items; see Table 1 for frequency).

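### The only specified ICER compares clinical integration with peer support, so it cannot show which of the three arms is most cost-effective

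*Combined protocol and SAP*

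**What the plan says.** The protocol's opening summary makes two economic commitments: "The cost-effectiveness of each approach will be assessed", and the research "aims to determine the most cost-effective strategy for implementing mHealth into primary healthcare systems". It also poses a narrower question: "The study is designed to isolate and examine the role of the clinician in delivering an mHealth system".

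The method appears once, in section 8.0 under Operational cost analysis. ICERs are to weigh up the "additional effectiveness achieved through clinical integration of the clinically integrated group compared to the peer-supported group". The sentence after that sets the unit of the main ICER (cost per drinking day reduced, over 12 months) and names no other comparator.

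Elsewhere, self-monitoring enters the economic work only through its costs or through outcomes taken one at a time:

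- Section 2.0 lists the secondary aim "Calculate the costs of health system use for each group".
- Section 6.0 plans a per-patient cost for all three groups.
- Section 8.0 (Intervention analyses) plans one model for cost and another for risky drinking, with pairwise group comparisons.

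**The concern.** All three arms receive Tula with the same static content (sections 1.0 and 5.0), so self-monitoring is both the control and a usable way of delivering the app. A search for the most cost-effective strategy has to include it.

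The ratio of clinical integration to peer support is the right decision ratio for clinical integration only if peer support is the next cheaper arm that is neither dominated (another arm costs no more and does at least as well) nor extendedly dominated (its ratio against the next cheaper arm exceeds that of the next more effective arm against it). The plan has no step that checks this. A health system could therefore be shown an attractive ratio against a comparator it would never choose, and peer support would have no ratio of its own. If further ratios are added later, the comparators will be chosen after the results are known.

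**Working it through.** **Inputs from the documents.** There are three arms, allocated 1:1:1 (section 7.0), which gives 3 × 2 / 2 = 3 pairwise contrasts. One has a specified ICER; the two involving self-monitoring have none. The documents give no expected costs or effects, so there is no figure of the plan's own to reproduce. Every cost and effect below is assumed.

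**Cost order 1: self-monitoring < peer < clinical.** Assume cost steps of 100 dollars, clinical avoiding 5 more drinking days than peer, and peer avoiding x more days than self-monitoring.

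- Planned ratio, clinical vs peer: 100 / 5 = 20 for every x.
- Peer vs self-monitoring: 100 / x, for x > 0.
- Clinical vs self-monitoring: 200 / (5 + x).

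| x | Planned ratio | Peer vs self-monitoring | Clinical vs self-monitoring | Status of peer | Relevant ratio for clinical |
|---|---|---|---|---|---|
| -5 | 20 | no gain | 200 dollars for no gain | dominated | none: clinical is dominated too |
| -2 | 20 | no gain | 200/3 = 66.7 | dominated | 66.7 |
| 0 | 20 | no gain | 200/5 = 40 | dominated | 40 |
| 2 | 20 | 100/2 = 50 | 200/7 = 28.6 | extendedly dominated | 28.6 |
| 4 | 20 | 100/4 = 25 | 200/9 = 22.2 | extendedly dominated | 22.2 |
| 6 | 20 | 100/6 = 16.7 | 200/11 = 18.2 | on the frontier | 20 |

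Peer is extendedly dominated when 100/x > 20, that is for 0 < x < 5. Above x = 5 the planned ratio is correct under this cost order.

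**Cost order 2: peer < self-monitoring < clinical.** The documents do not say that self-monitoring is the cheapest arm. Costs of health system use are to be calculated by group, and "Healthcare utilization will be collected from the self-reported medical services utilization form". If those costs are counted, this order is possible. Assume cost/days avoided of peer 100/0, self-monitoring 150/4 and clinical 300/8.

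- Self-monitoring vs peer: 50/4 = 12.5.
- Clinical vs self-monitoring: 150/4 = 37.5. The ratios rise, so all three arms are on the frontier and 37.5 is the relevant ratio.
- Planned, clinical vs peer: 200/8 = 25.

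With self-monitoring at 150/1 instead, its ratio against peer is 50/1 = 50 and clinical against it is 150/7 = 21.4. Self-monitoring is then extendedly dominated and 25 is correct.

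**Direction.** Suppose self-monitoring dominates peer, and clinical costs more and does more than self-monitoring. Replacing peer by self-monitoring as comparator cannot reduce the cost difference and cannot increase the effect difference, so the relevant ratio is at least the planned one. Under extended dominance in order 1, clinical vs self-monitoring is an effect-weighted average of the peer-vs-self-monitoring ratio and the smaller planned ratio, so it exceeds the planned ratio.

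**The case against.** The strongest reply is that this is a gap in specification, not a wrong analysis. The plan speaks of ICERs in the plural and calls one of them the main one, which suggests others. Section 2.0 lists no ranking aim, so the mismatch is with an introductory summary. Section 5.0 labels self-monitoring the control, so the strategy question could be read as peer versus clinical only. Costs and drinking outcomes are planned in every arm, so the missing ratios could be computed later.

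Part of this stands. The planned contrast is not wrong in itself, since it answers the clinician-role question, and no data would be lost. But no other comparator is named anywhere, and the narrower reading conflicts with giving every arm a version of Tula. The separate models with pairwise comparisons might hint at simple dominance but yield no cost per effect. Their drinking outcome, risky drinking, is also not the ICER's drinking days, although both can come from the same follow-back reports.

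Three further points are fair:

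- A frontier alone does not choose among the arms left on it; that needs a value per drinking day avoided, which the documents do not give.
- Removing arms on point estimates ignores sampling error.
- A 12-month total has to be extrapolated from 7-day reports at quarterly surveys, with weekly surveys only in the active period. The named sources for intervention cost are app log files and coach billing codes, with none named for peer-mentor time.

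The need for a value per day, the sampling error and the limits of the data apply equally to the planned ICER. They are reasons to add to the fix, not to leave self-monitoring out.

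**Conclusion.** The concern holds. Followed as written, the plan produces one ratio that cannot answer its own three-arm question. If peer support is dominated by self-monitoring or extendedly dominated, and clinical integration is costlier and more effective than self-monitoring, that ratio flatters clinical integration. It can also be the wrong ratio if self-monitoring lies between the other two on cost and is on the frontier.

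Confidence is high about the omission. The size and direction of any distortion in this trial are unknown. The 20 against 28.6 or 40, and the 25 against 37.5, rest wholly on assumed values, and other assumed values leave the planned ratio correct. The primary drinking and quality-of-life comparisons are not affected. The plan should be changed on this point, but the trial's main conclusions do not depend on it.

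**What to change.** In section 8.0, Operational cost analysis, specify a three-arm incremental analysis:

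1. Order the arms by observed mean cost, stating whether healthcare use is included.
2. Remove dominated and extendedly dominated arms.
3. Report each remaining arm's ICER, in cost per drinking day avoided over 12 months, against the next cheaper remaining arm.
4. Keep clinical versus peer as a separate line, labelled as the answer to the clinician-role question.

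Two additions would strengthen this: a statement of sampling uncertainty around the frontier, and results over a range of values per drinking day avoided.

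The cost is a little more analysis work. No new data collection is needed: per-patient cost and healthcare use are already planned for every arm, "patients in all three groups will be asked to complete (1) a weekly survey during the active intervention period" and then quarterly surveys, and "Patients will be asked to report on their drinking using the 7-day timeline follow-back". The plan should also say how 12-month drinking days are built from those reports, which the existing ICER needs in any case.
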